**Longitudinal Assessment of Bariatric Surgery (LABS-3):
Psychosocial Issues and Bariatric Surgery**

Design Synopsis

Hypotheses

1. Patients undergoing bariatric surgery will experience significant decreases in the rates of psychopathology, in particular depressive illness, and significant improvements in quality of life, post-operatively.
2. Untreated psychopathology that persists well beyond the surgery (e.g. to one-year follow-up) or that develops post-operatively will be associated with less weight loss and decreased quality of life.
3. Untreated psychopathology at the time of bariatric surgery, including affective disorders and substance abuse/alcohol abuse will be associated with increased short-term (e.g. 90 day) complications (e.g. problems with plugging, vomiting, and dehydration)
4. Syndromal/subsyndromal eating disorders prior to surgery including binge eating disorder and night eating syndrome will be associated with eating disorder symptoms and less weight loss at long-term follow-up.
5. Greater levels of affect dysregulation, greater deficits in cognitive control and greater deficits in reward processing will be associated with less favorable outcomes (higher affective disorder rates, less favorable net weight change, and increased eating disorder pathology/alcohol use pathology) following surgery.

Type of Study

- Prospective cohort study done at three (3) LABS centers.

Inclusion Criteria

- Male and female patients who are at least 18 years of age and undergo bariatric surgery by a LABS certified surgeon.
- Previous enrollment in LABS-1 and LABS-2.
- BMI at baseline of greater than or equal to 35.

Exclusion Criteria

- Informed consent not obtained
- Type 1 Diabetes Mellitus
- Unlikely to comply with follow-up protocol (ie: geographically inaccessible for study visits)
- Unable to communicate with local study staff

Sample Size

- In order to sample a sufficient number of subjects with significant psychopathology at baseline, the sample size for the assessment of psychopathology is 250. The assessment of eating behavior will be done on a subset of 100 subjects.

Duration of Follow-up

- Up to 7 years following bariatric surgery

Outcomes

- Changes in medical and psychosocial measures

Data Collection Schedule

- The LABS-3 Psychosocial baseline data will be collected within 30 days prior to bariatric surgery.

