3.2.4 Criteria for Study Withdrawal

- Patient withdraws consent
- The Principal Investigator or NIDDK ends the study

3.3 Enrollment Procedures. Once a candidate for LABS-3 Psychosocial has been identified, study details will be carefully discussed with the patient by a member of the LABS staff. All study related procedures will be explained and questions about the research protocol will be answered. If the patient agrees to participate, the study coordinator or Principal Investigator will go through the informed consent process with the patient. The patient will be asked questions to assure a thorough understanding of the consent document. Once a patient has consented to LABS-3 Psychosocial, they will be enrolled into the protocol.

3.4 Study Visits and Database Contents. Patients will be scheduled 1-30 days prior to surgery for their LABS-3 Psychosocial baseline evaluation at the Neuropsychiatric Research Institute, at the University of Pittsburgh Medical Center and at Cornell/Columbia in New York. Complete follow-up data collection will occur at approximately 12 months, and annually following surgery, along with a brief follow up assessments at 6 months and 18

months following surgery. There will also be data collected about weight loss, and psychological and quality of life measures that will be obtained from the LABS-2 database. All data are collected during an in-person visit, by phone assessment, or by accessing the LABS-2 data set. The tables below indicate the schedule of measures by study visit. A copy of all measures is included in the Appendix. New measures/ tasks are being incorporated for one time administration at the 7 year follow up time point. The new measures/ task will be accessible online for participant convenience which allows for the ability to complete these at home.

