3.4.1 Clinical Forms and Interview Schedule

Measure/Test	Form Details	Baseline/ Presurgery	6 month follow up	12 month follow up	18 month follow up	annual follow up
PSYCHOPATHOLOGY N= 250						
INTERVIEW						
SCID/IP	Structured Clinical Interview for DSM-IV	X				X
EDE- BSV	Eating Disorders Examination- Bariatric Surgery Version	X		X		X
M-FED-BSV	MFED- Bariatric Surgery Version	X	X	X	X	
SELF-REPORT						
BDI*	Beck Depression Inventory	X	X	X		X
SF-36*	Short Form-36	X	X	X		X
IWQOL- Lite	Impact of Weight on Quality of Life- Lite	X*	X	X*		X*
PETS	Psychiatric and Emotional Test Survey	* X	X	* X	X	* X
MED	Medication Form	* X	* X	* X	X	* X
CTQ	Childhood Trauma Questionnaire					X (one time)
EATING BEHAVIOR N= 100						
NDS	48 Hour Dietary Recall- Nutritional Data System	X	X	X		X

* Gathered as a part of LABS-2

INTERVIEW SCHEDULE WITH NEW MEASURES AND TASKS AT YEAR 7:

LABS Baseline and F/U Funding for Part of Cohort						RO1 Funding				
	Pre-surg	6 mo	1 yr	18 mo	2 yrs	3 yrs	4 yrs	5 yrs	6 yrs	7 yrs
INTERVIEW										
SCID/IP	X				X	X	X	X	X	X
EDE-BSV	X		X		X	X	X	X	X	X
M-FED-BSV		X	X	X	X	X	X	X	X	X
72-hour dietary recall (NDS-R)	X	X	X		X	X	X	X	X	X
SELF-REPORT										
Administered as a part of LABS 2*	X	X	X	X	X	X	X	X	X	X
The following have been added as a new, separate final visit.										
DERS										X
AIM										X
UPPS-P										X
ATQ-ECS										X
SPSRQ										X
Go/No-Go Task										X
Delay Discounting Task										X

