c. Hypothesis #3. Hypothesis #3 states that untreated psychopathology at the time of bariatric surgery will be associated with increased short-term complications. A logistic regression analysis will be used to evaluate the influence of psychopathology at the time of surgery on short-term surgical complications. Analyses will evaluate the impact upon both DSM-IV diagnostic psychopathology (e.g., current mood disorder, current anxiety disorder, current substance use disorder, any Axis I disorder, any Axis II disorder) and a continuous measure of depressive symptoms, the BDI, upon short-term post-surgical complications.

d. Hypothesis #4. Hypothesis #4 posits that syndromal or subsyndromal eating disorders prior to surgery will be associated a greater frequency of eating disorder symptoms and less weight loss at long-term follow-up. Data from the EDE-BSV and the NDS dietary recall will be aggregated to determine the frequency of various eating disorder symptoms (binge eating, grazing, vomiting, chewing and spitting) at each assessment point. RRM's will then be used to evaluate the effect of pre-surgical eating disorder syndromes (including binge eating disorder and night eating) on eating disorder frequency (Poisson-based RRM) and BMI (linear RRM). The basic models will include a random effect for subject, and fixed effects for site, assessment time, time-by-site interaction, and pre-surgical eating disorder diagnoses (both syndromal and subsyndromal diagnoses).

Power Analysis and Sample Size

Hypothesis #1. Power analyses below assume an attrition rate of 15% at 12 months, and a 10% attrition rate at 24 month assessments. An enrolled sample size of 250 would provide an estimated sample size of 213 at 12 months and 191 at 24 months.

Power analyses regarding the reduction of psychopathology following surgery is based on the finding of Glinski et al. (2001) that 50% of pre-bariatric surgery candidates meet criteria for at least one current Axis I disorder. Assuming a conservative two-tailed alpha of .01, the proposed sample size would provide a power of .90 to detect a reduction in psychopathology of just over 10% from pre-surgery at 12 months and 12% at 24 months (Hintze, 2001). These reductions for Axis I disorders are consistent with those reported in the literature following bariatric surgery (Herpetz et al. 2004).

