Effect size estimates for changes in quality of life and depression scores after post-surgery are taken from the Utah Obesity Surgery Study (Adams et al., 2005). A total of 224 bariatric surgery patients were evaluated using the IWQOL-Lite and SF-36 prior to surgery and at 1-year follow-up. The IWQOL-Lite total score improved from 32.4 ± 16.1 pre-surgery to 86.6 ± 16.1 at 1-year follow-up (effect size = 3.37); the SF-36 mental component, which is highly correlated with measures of depression, improved from 41.1 ± 6.4 pre-surgery to 44.8 ± 6.4 at 1-year follow-up (effect size = .58); the SF-36 physical component improved from 35.4 ± 6.5 pre-surgery to 45.2 ± 5.8 at 1-year follow-up (effect size = 1.51). Power estimates assume a conservative two-tailed alpha of .01, a correlation between pre-surgical and follow-up assessments of .50, and differences between pre-surgical and post-surgical assessments in quality of life and depression comparable to those from the Utah study. The proposed sample size would provide a power of greater than .98 to detect these differences between pre-surgical and subsequent post-surgical assessments quality of life and depression scores at each follow-up assessment (Hintze, 2001).

Hypothesis #2. Power analyses for Hypothesis #2 are based upon a study by Averbukh et al. (2003) reporting a correlation between pre-surgical BDI score and subsequent weight loss of .397, corresponding to an effect size (d) of .64 (Cohen, 1988; p. 82). Power analysis for this hypothesis is based upon the procedures described by Hedeker and colleagues (Hedeker, et al., 1999) for longitudinal random effects models with attrition. Power analyses assume a conservative two-tailed alpha of .01, a 50% rate of pre-surgical Axis I disorder, and 4 observation points (6, 12, 18 and 24 months), and a correlation of .30 between observations.

Power analyses focus on the differences weight loss between those individuals with and without pre-surgical psychopathology. The proposed sample size will provide a power of approximately .95 to detect an attrition-adjusted effect size of .64 (Hedeker et al., 1999).

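### The schedule gives no SCID at 12 months, yet the protocol states power for a 12-month fall in Axis I disorders and describes that visit as complete

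*Protocol*

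**What the plan says.** **Analysis and power.** In section 4, Hypothesis 1 is tested partly with a logistic random regression model for current mood, anxiety and substance use disorder, with Bonferroni contrasts of each later assessment against baseline. The power section claims .90 at two-sided alpha .01 to "detect a reduction in psychopathology of just over 10% from pre-surgery at 12 months", and to detect 12% at 24 months. It assumes 213 and 191 patients remaining of 250.

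The Design Synopsis opens Hypothesis 2 with "Untreated psychopathology that persists well beyond the surgery (e.g. to one-year follow-up" and adds psychopathology that arises after surgery. The Hypothesis 2 model in section 4 enters current diagnoses as time-varying covariates. Its power paragraph assumes "4 observation points (6, 12, 18 and 24 months), and a correlation of .30 between observations".

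**Schedule.** Section 3.4.2 names the SCID as the interview for Axis I disorders. In the first table of section 3.4.1 its row reads "SCID/IP Structured Clinical Interview for DSM-IV X X"; the two marks stand under baseline and annual follow-up. In the second table, which has a column for each year, the row reads "SCID/IP X X X X X X X"; the seven marks stand under pre-surgery and years 2 to 7.

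**Narrative.** Section 3.4 says: "Complete follow-up data collection will occur at approximately 12 months, and annually following surgery". It calls the 6- and 18-month assessments brief. Section 2.1 allots three hours to baseline, 12 months and annual visits alike, and 30 minutes to months 6 and 18.

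**The concern.** A power statement implies that the outcome will be measured at the visit it names. Here the instrument that defines the outcome is not scheduled at that visit, and the narrative suggests that it is. A site working from the tables would not give the interview at month 12, and the power section would then describe a comparison that cannot be made.

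The choice between 12 and 24 months also has substance. Section 1.1 cites reports that mood and anxiety problems return about two years after surgery, and section 2.1 expects some psychopathology to re-emerge at 18 to 24 months. If the first post-surgical diagnosis is taken at 24 months, early improvement followed by relapse cannot be told apart, by SCID, from no improvement.

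**Working it through.** **1. The plan's sample sizes.** Inputs from the Hypothesis 1 power paragraph are 250 enrolled, 15% attrition by 12 months and a further 10% by 24 months.
- 12 months: 250 × 0.85 = 212.5, stated as 213.
- 24 months: 250 × 0.85 × 0.90 = 191.25, stated as 191.

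Both reproduce.

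**2. The plan's power.** The baseline rate is 50% and alpha is .01 two-sided. The protocol gives no within-person correlation φ for the diagnosis, so φ has to be assumed. For a paired (McNemar) comparison with p0 = .5, p1 = .5 − d, discordance D = p0 + p1 − 2·p11 and p11 = p0·p1 + φ·√[p0(1−p0)p1(1−p1)]:

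power = Φ{ (d√n − 2.576·√D) / √(D − d²) }

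With n = 213, d = .105 and φ = .70, D = .158 and power = .91. With d = .10 it is .87. The smallest falls detectable with power .90, in percentage points, are:

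| Assumed φ | 12 months, n=213 | 24 months, n=191 |
|---|---|---|
| .70 | 10.4 | 11.0 |
| .65 | 11.2 | 11.8 |
| .50 | 13.3 | 14.1 |
| 0 | 18.5 | 19.5 |

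The stated figures are within reach at φ of about .65 to .70. The point here is therefore not the arithmetic but whether the 12-month data will exist.

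**3. SCID marks, column by column.**

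| Visit | Table 1 | Table 2 |
|---|---|---|
| Pre-surgery | yes | yes |
| 6 months | no | no |
| 12 months / 1 year | no | no |
| 18 months | no | no |
| Annual / years 2–7 | yes (annual) | yes (each year) |

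**4. Does annual in table 1 include month 12?** No. The EDE-BSV row, "Eating Disorders Examination- Bariatric Surgery Version X X X", is marked at baseline, at 12 months and in the annual column; the BDI and SF-36 rows are also marked in both of the last two. Table 2 leaves the 1-year cell blank for the SCID and fills it for the EDE-BSV. The two tables have different layouts and agree, so a reading error in one is unlikely to explain the gap.

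**5. Could another instrument supply the diagnosis?** PETS and the M-FED-BSV are scheduled at 12 months. Section 3.4.3 describes PETS as a consortium questionnaire, and section 3.4.2 describes the M-FED as recording other treatment received. Neither is said to yield DSM-IV diagnoses. Nothing says that the 24-month SCID will date disorders back to month 12. Section 1.1 argues that sound diagnoses need structured interviews such as the SCID.

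**6. Result if the tables hold.** Scheduled SCID diagnoses at 12 months: 0, against 213 assumed. First post-surgical SCID: 24 months, planned n = 191. Post-surgical SCIDs available to Hypothesis 2: years 2 to 7.

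**The case against.** **The tables may be the part in error.** The narrative gives month 12 the same three hours as baseline, when the SCID is given. The tables also disagree with each other elsewhere: the M-FED-BSV is marked at baseline only in table 1 and at years 2 to 7 only in table 2, and the dietary recall is 48 hours in one and 72 in the other. This stands. The documents show a contradiction; they do not prove that the SCID was never intended at month 12.

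**The analysis text names no 12-month diagnosis contrast.** It compares baseline with later assessment points, which the SCID supplies from year 2. That limits the damage, but the power paragraph does name 12 months and attaches a sample size to it.

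**Hypothesis 2 does not fix one year.** One year is only an example in the synopsis, and the analysis text sets no such criterion. This stands too: the hypothesis remains testable from 24 months.

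**What a reader might infer about Hypothesis 2 power.** A reader might conclude that three of its four observation points lack an exposure, and derive an inflated standard error from the .30 correlation. The documents do not support this. That calculation compares patients with and without pre-surgical psychopathology, which the baseline SCID supplies; the four points are weight outcomes. A formula for fixed groups would also not suit a time-varying diagnosis, and a 24-month horizon would ignore the SCIDs at years 3 to 7.

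**What a reader might infer about lost records.** Nor does it follow that all BMI and quality-of-life records at 6, 12 and 18 months leave the model. How visits without a concurrent diagnosis are handled is commonly left to an analysis plan, and table 1 marks no SF-36 or IWQOL-Lite at 18 months.

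**Conclusion.** The point holds as an internal contradiction with a definite consequence. If the schedule tables are followed, one of the two powered diagnosis contrasts of Hypothesis 1 (12 months, n = 213) has no data. The diagnosis covariates of Hypothesis 2 are unobserved before 24 months, so neither persistence nor onset at one year can be seen by SCID. This assumes that the tables govern and that no other 12-month instrument yields Axis I diagnoses; the protocol names none.

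The 24-month diagnosis contrast, the 12-month BDI, SF-36 and IWQOL-Lite contrasts, and the Hypothesis 2 power figure stand. It would be too strong to say that Hypothesis 1 cannot be tested at one year, or that Hypothesis 2 loses its power basis.

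**What to change.** Make the schedule and the text agree, by one of two routes.

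1. **If the SCID belongs to the 12-month visit,** mark it at 12 months in table 1 and at 1 year in table 2. The power statement, the narrative and the one-year example can then stay. This version already adds year-7 measures, so for participants whose 12-month visit has passed the correction can only record interviews that were actually done.
2. **If the tables are right,** delete the 12-month diagnosis power statement and name 24 months as the first diagnosis contrast. Change the one-year example in Hypothesis 2 to 24 months, and restrict the SCID time-varying covariates to years 2 to 7. Use the BDI, already collected at 6 and 12 months, as the early measure of psychopathology. Amend sections 2.1 and 3.4 so that month 12 is not described as a full assessment that includes the SCID.

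The second route costs wording only and needs no new visit. Its price is that the earliest diagnosis result moves from 12 to 24 months, and the BDI covers depressive symptoms rather than anxiety or substance use disorder.

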Hypothesis #3. Power analysis estimates for Hypothesis #3 are based upon a study by Powers et al. (1988) reporting an association between the presence of pre-surgery Axis I diagnosis and post-surgical complications. All 9 (100%) patients with a pre-surgical Axis I diagnosis experienced post-surgical complications, compared to 7 of 15 (47%) of those without a pre-surgical Axis I diagnosis (contingency coefficient = .42). It would be unrealistic to expect that every patient with an Axis I disorder would develop post-surgical complications. However, if we assume that 80% of those with an Axis I disorder would develop complications post-surgery, and further assume a conservative two-tailed alpha of .01, the proposed sample size of 250 enrolled patients would provide a power of .98 to detect this association and would provide a power of .80 to detect a contingency coefficient of .165 (Hintze, 2001).

Hypothesis #4. Power analysis for Hypothesis #4 is based upon a study of Hsu et al. (1996) reporting an association between pre-surgical eating disturbance and weight regain post-surgery. They report that 8 of 19 (42%) patients with pre-existing eating disturbance regained weight after surgery, compared to 0 of 5 (0%) without a pre-existing eating disturbance (contingency coefficient = .341), corresponding to an effect size (d) of .57. Power analyses assume a conservative two-tailed alpha of .01, a 50% rate of pre-surgical eating disturbance, and 5 observation points (6, 12, 18 and 24 months), and a correlation of .30 between observations. Power analyses focus on the differences weight loss between those individuals with and without pre-surgical psychopathology. The proposed sample size of 100 subjects for the assessment of eating behavior will provide a power of approximately .88 to detect an attrition-adjusted effect size of .57 (Hedeker et al., 1999).

5 Study Organization

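### Hypothesis 3: the power to detect a contingency coefficient of .165 with 250 patients at alpha .01 is about .53, not .80

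*Protocol*

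**What the plan says.** The statement is in Protocol section 4, under Power Analysis and Sample Size, Hypothesis #3. The planning scenario comes from a small earlier study in which all 9 patients with an Axis I diagnosis had complications, "compared to 7 of 15 (47%) of those without a pre-surgical Axis I diagnosis (contingency coefficient = .42"). The protocol treats 100% as unrealistic and assumes instead that "80% of those with an Axis I disorder would develop complications post-surgery".

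The test conditions come next: "further assume a conservative two-tailed alpha of .01, the proposed sample size of 250 enrolled patients". Under those conditions the same sentence makes two claims. The first is power .98 for the 80% scenario. The second is that the sample "would provide a power of .80 to detect a contingency coefficient of .165". No other alpha, sample size or attrition allowance is given for the second claim.

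**The concern.** The two claims do different jobs. The 80% versus 47% scenario is a very large effect, so high power there says little about moderate associations. The .165 figure is the section's only guide to the smallest association between one binary predictor, such as any Axis I disorder, and complications that the study could reliably detect.

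At N = 250 and alpha .01, an effect of about .17 on the w scale looks too small for power .80. If the figure is wrong, a null result would be read as fairly strong evidence against an association of that size when the data could not support that reading. The protocol's background section names the association between Axis I disorder and complications as a finding it aims to replicate, so a null result would matter.

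**Working it through.** **Inputs, all from the Hypothesis #3 power paragraph**
- Alpha: .01, two-sided ("further assume a conservative two-tailed alpha of .01").
- Sample size: N = 250 ("the proposed sample size of 250 enrolled patients").
- Effect: contingency coefficient C = .165.
- Stated power: .80.

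**Which coefficient is meant.** Pearson's coefficient is C = √(χ²/(χ² + N)). The power section prints two values that can be checked against it.
- Hypothesis #4, 8 of 19 versus 0 of 5: χ² = 3.158, so C = √(3.158/27.158) = .341, as printed.
- Hypothesis #3, 9 of 9 versus 7 of 15: the continuity-corrected χ² is 5.0, so C = √(5/29) = .415, printed as .42. Without the correction, χ² = 7.2 and C = .480.

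The protocol is therefore using Pearson's C, and the standard conversion to Cohen's w applies.

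**Attempt to reproduce the stated power**
- w = C/√(1 − C²) = .165/√(1 − .0272) = .1673.
- Noncentrality: λ = N·w² = 250 × .02799 = 7.00.
- Critical value of χ² on 1 df at .01: 6.635.
- Power = P(noncentral χ²₁ with λ = 7.00 exceeds 6.635) = **.528**.

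A two-proportion calculation with 125 per group and the same w gives .528. Simulation of the 2×2 table gives .521.

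**Other readings tried**

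| Reading | Power |
|---|---|
| .165 taken directly as w, alpha .01 | .513 |
| Fisher-z test of a correlation of .165, alpha .01 | .516 |
| One-sided alpha .01 | .625 |
| Two-sided alpha .05 | .753 |
| Two-sided alpha .10 | .841 |
| N = 213 or 191 (the attrition-reduced numbers given for Hypothesis #1), alpha .01 | .447 or .396 |
| 2 to 4 degrees of freedom, alpha .01 | .42 to .30 |
| .165 as a difference in proportions from 47%, alpha .01 | .52 |

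None gives .80. A difference in proportions of .165 comes close (.794) only from a 10% comparison rate, which the protocol does not use and which is not a coefficient of .165. The share of patients with an Axis I disorder cannot explain the gap either, because C already reflects the margins of the table.

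**What 250 patients can detect**
- w for power .80 at alpha .01: (2.576 + .842)/√250 = .216.
- C = w/√(1 + w²) = .216/√1.0467 = **.211**.
- At alpha .05 the corresponding C is .174, and at .10 it is .155. No conventional alpha gives .165.

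**Sample size for C = .165.** (3.418/.1673)² is about 417.3, so **418** patients.

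**In percentages.** This needs an exposure share, which the Hypothesis #3 paragraph does not give. I assume half exposed, in line with the rate quoted under Hypothesis #1 ("50% of pre-bariatric surgery candidates meet criteria for at least one current Axis I disorder"), and 7/15 with complications among the unexposed. Then C = .165 is about 63% versus 47%, and C = .211 is about 68% versus 47%. With the source study's split of 9 exposed in 24, the upper figures are about 64% and 69%.

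**The other claim in the sentence.** For 80% versus 7/15 with half exposed, power at alpha .01 is above .99, so the printed .98 is not overstated under that assumption.

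**The case against.** The arithmetic is hard to dispute: alpha, sample size, power and coefficient stand together in one legible sentence, and nothing elsewhere in the protocol corrects them. The fair objections concern weight.

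- **It is a secondary figure.** The synopsis justifies 250 by the need for enough patients with psychopathology at baseline, not by the .165 statement, and the main scenario for Hypothesis 3 is adequately powered. This stands. No analysis, endpoint or eligibility rule depends on the number.
- **It does not describe all of Hypothesis 3.** The planned analysis is logistic regression on several diagnostic groupings and on the continuous BDI score, whereas a contingency coefficient describes a single two-by-two table. This also stands. The figure should be read as the limit for one binary predictor.
- **Nothing says .165 will be used to interpret a null result.** True, but stating a detectable effect has little other purpose, and the printed figure is wrong whatever use is made of it.
- **The percentage translation needs an exposure share taken from elsewhere in the power section.** True, and it is labelled as an assumption above. The correction itself does not depend on it.

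**Conclusion.** The stated power is wrong. For a contingency coefficient of .165, with 250 patients and a two-sided alpha of .01, it is about .53, an overstatement of about 27 percentage points. The chance of missing an association of that size is about 47%, not the implied 20%. The coefficient detectable with power .80 is about .21.

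The result rests on a 1-df chi-square test and on Pearson's definition of the coefficient, which the protocol's own worked values support. It also takes all 250 patients as contributing an outcome; any loss would lower the power further. The error is confined to this one statement.

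**What to change.** In the Hypothesis #3 paragraph, correct one of the two numbers. Either state that 250 patients at a two-tailed alpha of .01 give power .80 for a contingency coefficient of about .21, or keep .165 and give its power as about .53. If a translation into complication rates is added (about 68% versus 47% for .21), state that it assumes half the cohort is exposed and a 47% rate in the unexposed. It would also help to say that the figure refers to a single binary predictor.

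The cost is one corrected, less favourable figure. Enrolment, data collection and the planned analysis stay as they are.

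### The stated powers for Hypothesis 2 (.95) and Hypothesis 4 (.88) cannot both hold under their common settings; .88 is about right, and .95 fits about 100 enrolled, not 250

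*Protocol*

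**What the plan says.** Both calculations are in Protocol section 4, under Power Analysis and Sample Size.

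- **Hypothesis 2.** The assumptions are two-tailed alpha .01, a 50% rate of pre-surgical Axis I disorder, "4 observation points (6, 12, 18 and 24 months") and correlation .30. The proposed sample size "will provide a power of approximately .95 to detect an attrition-adjusted effect size of .64". The paragraph prints no N. The Design Synopsis and the Hypothesis 1 power paragraph give 250.
- **Hypothesis 4.** The assumptions are the same alpha, "a 50% rate of pre-surgical eating disturbance" and "5 observation points (6, 12, 18 and 24 months), and a correlation of .30 between observations". The effect is taken from an earlier pilot study, "corresponding to an effect size (d) of .57". The sample of 100 "will provide a power of approximately .88 to detect an attrition-adjusted effect size of .57".

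Both paragraphs cite the same procedure for longitudinal models with attrition. The attrition rates appear under Hypothesis 1: 15% by 12 months and a further 10% by 24 months, so 250 becomes 213 and then 191.

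The planned models are under Hypothesis Testing in the same section. For Hypothesis 4 the pre-surgical eating disorder diagnosis is a fixed effect beside site, time and time-by-site. For Hypothesis 2 psychopathology enters as a time-varying covariate. Neither basic model lists an interaction of the psychiatric or eating diagnosis with time.

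**The concern.** Hypothesis 4 has two-fifths of the sample of Hypothesis 2 and a smaller target effect, yet its power is only .07 lower. With every other setting shared, the gap should be far wider, so at least one figure is wrong or something differs between the paragraphs that is not disclosed. In addition, the two paragraphs list the same four months but count them differently, as four and as five.

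The consequence is that a reader cannot tell from the page what either power refers to. The protocol's data and safety monitoring section relies on all parts of the study having been powered with drop-outs in mind, so the figures should be reproducible from the inputs printed with them.

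**Working it through.** **Inputs.** Alpha .01 two-sided (critical value 2.576), 50:50 split, correlation .30, d = .64 (Hypothesis 2) and .57 (Hypothesis 4). N is 250 and 100. Retention is .85 at 12 months and .85 × .90 = .765 at 24 months. Retention at 6 and 18 months is not given, so a range is used.

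**Step 1: comparison without choosing a contrast.** If method, contrast and attrition pattern are common to both hypotheses, the signal-to-standard-error ratio λ scales with d√N.

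- Implied by the printed powers: Hypothesis 2, 2.576 + 1.645 = 4.221. Hypothesis 4, 2.576 + 1.175 = 3.751. Ratio 1.125.
- Required by the inputs: .64 × √250 = 10.12 against .57 × √100 = 5.70. Ratio 1.775 (about 1.71 if Hypothesis 4 really has five visits).
- Effect sizes alone: .64/.57 = 1.123.

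The printed pair therefore behaves as though both hypotheses had the same N. If .88 were right, Hypothesis 2 would have λ = 3.751 × 1.775 = 6.66 and power above .999.

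**Step 2: direct calculation for a constant group difference at the four listed visits.** With equal correlation ρ, a patient with k visits contributes k/(1 + (k − 1)ρ) units of information: 1, 1.538, 1.875 and 2.105 for k = 1 to 4. If p_k is the share of enrolled patients with k visits,

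I = Σ p_k × k/(1 + (k − 1)ρ), λ = d√(N × I/4), power = Φ(λ − 2.576).

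Three retention patterns at 6, 12, 18 and 24 months:

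- A, 24-month N at every visit (.765 throughout): I = .765 × 2.105 = 1.611.
- B, stepwise (.85, .85, .765, .765): I = .085 × 1.538 + .765 × 2.105 = 1.741.
- C, gradual (.925, .85, .8075, .765): I = .075 × 1 + .0425 × 1.538 + .0425 × 1.875 + .765 × 2.105 = 1.831.

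| Pattern | Hypothesis 4, N = 100, d = .57 | Hypothesis 2, N = 250, d = .64 | Hypothesis 2 effect with N = 100 |
|---|---|---|---|
| A | λ 3.617, power .85 | λ 6.421, above .999 | λ 4.061, power .93 |
| B | λ 3.761, power .88 | λ 6.677, above .999 | λ 4.223, power .95 |
| C | λ 3.856, power .90 | λ 6.846, above .999 | λ 4.330, power .96 |

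Pattern B reproduces both printed figures, .88 and .95, with four visits, one contrast and 100 enrolled in each. Working backwards gives the same answer. With four complete visits, total N = 4 × .475 × (λ/d)², where .475 = (1 + 3 × .30)/4. That is 82.6 analysed patients for .95 at d = .64, and 82.3 for .88 at d = .57.

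**Step 3: the fifth observation point.** Five visits with 76.5 analysed patients give λ = .57 × √(76.5/(4 × .44)) = 3.758, power .88, where .44 = (1 + 4 × .30)/5. So .88 can be reached with five visits, but pattern B reaches it with four.

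**Step 4: a linear group-by-time contrast.** Let the difference grow from 0 at the first visit to d at the last. With complete data λ = (d/3)/√(4 × .70/(5N)).

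- Hypothesis 2, N = 191.25: .2133/.0541 = 3.94, power .91 (.93 under pattern C).
- Hypothesis 4, N = 76.5: .19/.0856 = 2.22, power .36 (.39 under pattern C).

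This contrast brings Hypothesis 2 near .95 but puts Hypothesis 4 far below .88. Neither of the two contrasts, held common, gives both printed figures at 250 and 100.

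**The case against.** **The error, if any, is conservative.** Under the planned form of analysis .88 is right to within about .03, and the faulty figure, .95, is too low. No sample size or conclusion turns on it. This stands, and it limits the weight of the point. It does not make the two paragraphs consistent.

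**The Hypothesis 2 paragraph does not print 250.** That is true. The figure is inferred from the Design Synopsis and the Hypothesis 1 paragraph. But no other sample size is given for the psychopathology cohort, and if another N was used the paragraph should say so.

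**The contrast may have differed.** The reference list describes the cited method as concerned with time-related contrasts between two groups, so a trend test cannot be excluded. A reader might go on to infer that Hypothesis 4 has less than even power: .36 to .39 for a trend, or .42 if .95 is taken as correct (4.221/1.775 = 2.378, and Φ(2.378 − 2.576) = .42). The documents do not support that. The basic model for Hypothesis 4 has a diagnosis main effect and no diagnosis-by-time term, so those values belong to a test the protocol does not plan. The change-of-contrast explanation is also unnecessary, because one contrast and one N reproduce both figures.

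**The .88 may seem to depend on the unlisted fifth visit.** A reader might infer this because five visits with the 24-month N give .88. Four visits with stepwise attrition give it too, so the miscount need not have driven the result. It remains a miscount.

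**The effect sizes are called attrition-adjusted, so full enrolment might be the right N.** With no attrition and four visits, Hypothesis 4 would be .94 and Hypothesis 2 still above .999. That reading does not reconcile the pair either.

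**Conclusion.** The point holds as an inconsistency between two printed powers, together with a miscounted or incomplete list of visits. Under the shared settings the figures imply a signal ratio of 1.125 where 250 and 100 enrolled require about 1.78.

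For a constant group difference, Hypothesis 4 has power of about .85 to .90, so the stated .88 is about right. Hypothesis 2 at 250 exceeds .999, so the stated .95 is too low. The simplest explanation is that .95 was computed for about 100 enrolled, but the document does not show how it arose.

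This rests on four assumptions: N = 250 for Hypothesis 2, equal correlation of .30 between visits, the protocol's own attrition rates applied to both samples, and assumed retention at 6 and 18 months, which accounts for the range. It is not a finding that Hypothesis 4 is underpowered for its planned analysis.

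**What to change.** In the two power paragraphs of section 4:

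1. Under Hypothesis 4, change the count to the four listed visits, or name the fifth.
2. State the N and the contrast, a constant group difference, for both hypotheses.
3. Restate Hypothesis 2 as above .99 at 250 enrolled, or say that .95 refers to about 100 enrolled.
4. Give Hypothesis 4 as about .85 to .90, with the retention assumed at 6 and 18 months.
5. Only if a linear group-by-time contrast is really intended, say so, add the term to the models, and give about .91 to .93 for Hypothesis 2 and .36 to .39 for Hypothesis 4.

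Items 1 to 4 change wording only, with no effect on enrolment, visits or analysis. Item 5 would change the planned models and show Hypothesis 4 to be underpowered, so it should be taken up only if that contrast was the one meant.
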